#### ADVERSE EVENTS

An AE is any unfavorable or unintended sign, symptom or disease occurring in a participant at any stage of the study, whether or not considered related to the study.

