#### CLINICAL ENDPOINTS

Any reported AEs that meet the following are also clinical endpoints and will be reported on the End of Study form. DMC Project Manager will review all AEs to determine if they also meet

clinical endpoint criteria. If criteria are met, the DMC Project Manager will ensure all documentation need for endpoint review is received by the site study coordinator.

	Anticipated A	Adverse Events (AAE)	Unanticipated Adverse Events (UAE)			
	
 
Headaches
 
	
 
Oxygen saturation less
 
	
 
Any Adverse effect
 
	
 
Any event that
 
		
	o Fever	than 90 during the	on the health or	results in death		
	o Chills	monitoring period	safety caused by, or	o Conversion of		
	
 
Loss of appetite
 
	
 
Absolute reduction in
 
	associated with, the	family members		
	o Nausea	oxygen saturation of more	CPAP or progression	to COVID		
	
 
Vomiting
 
	than 4% associated with	of underlying COVID	positive in the		
	o Fatigue	shortness of breath or	that was not	CPAP group		
	
 
Muscle or body aches
 
	difficulty breathing	previously identified			
	
 
New loss of taste or smell
 
	o Persistent pain or pressure	in the product			
	
 
Sore throat
 
	in the chest	labeling, published			
	
 
Congestion or runny nose
 
	
 
Any worsening of COVID
 
	literature or study			
	
 
Diarrhea
 
	symptoms that lead to an	protocol			
	
 
Decrease in oxygen
 
	Emergency room visit,				
	saturation (that is not	hospital admission, ICU				
	associated with shortness	admission, intubation, or				
	of breath or difficulty	mechanical ventilation				
	breathing)					
Reporting	None	Redcap	None	Redcap, DSMB, IRB		

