Early Continuous Positive Airway Pressure (CPAP) in COVID-19 Confirmed or Suspected Patients

PI: [name], MPH

NCT04390191

Document Date: 4-21-2020

General Design Issues

This is a prospective, single-center, parallel group, open-label, randomized clinical trial. The primary objective is to evaluate the efficacy and safety of the use of CPAP versus control in COVID-19 suspected or confirmed patients with pneumonia or respiratory illness. The primary efficacy endpoint is a **non-weighted composite endpoint comprised of the following components:**

- All-cause mortality within 14 days of randomization
- Hospital Admission (including ED visit) within 14 days of randomization
- Oxygen saturation less than 90 during the 72-hour observation period from randomization
- Absolute reduction in oxygen saturation of more than 4% during the 72-hour observation period from randomization

Sample Size and Power

Sample size was restricted by the availability of CPAP and the need for rapid answers during the exceptional health care challenges and fluid epidemiological conditions. The table below summarizes the effect sizes (% reduction in the proportion of patients with a negative outcome) that can be detected with sufficient power (>80%) under several scenarios assuming a total sample size of 200 patients (100 per arm) using a two-sided Fisher's exact test at the 0.05 significance level. Preliminary data from the Mount Sinai Health System indicated that about 25% of the COVID-19 positive patients with respiratory distress were sent home and subsequently hospitalized. We assumed that the proportion of patients with a negative outcome in the control group will range between 25% to 50%. Depending on these values, the planned sample size will allow us to detect a relative treatment reduction between 64% to 42% in this range (see table below).

Furthermore, given the short follow-up time for the assessment of the primary outcome and the nature of the primary outcome, we anticipate that we will be able to assess the primary outcome on all patients. We also believe that patients will be supportive of this intervention and compliant with treatment, so sample size was not adjusted for drop-out rates. However, if due to unforeseen circumstances we will conservatively set any missing primary outcome assessment to "negative" or "failure". Power calculations were performed in SAS 9.4 using the PROC POWER function.

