Proportion of patients with Negative outcome	Control	0.25	0.30	0.35	0.4	0.45	0.5
	СРАР	0.09	0.12	0.16	0.20	0.25	0.29
	Relative reduction in CPAP arm (%)	64	60	54	50	44	42

Randomization Design and Procedure

Patients will be randomized using a 1:1 allocation to CPAP versus control group. The randomization will be stratified by BMI ($\geq=30$ and ≤30), gender and age (≤60 , $\geq=60$). A random permuted block design will be employed, with random blocks of size 2 and 4.

Data Monitoring and Analysis

Primary Efficacy Analysis

The primary efficacy endpoint is the proportion of patients with a negative composite endpoint within 14 days of randomization and will be compared between CPAP and control groups. The null hypothesis is that the proportion of patients with a negative outcome will be the same between patients randomized to CPAP versus control arm. This hypothesis will be tested using a two-sided Fisher's exact test at 0.05 alpha level. The primary analysis will be conducted according to the intention-to-treat principle.

Early stopping rule: If three deaths are observed in the CPAP group, enrollment will be halted pending DSMB review and recommendations. As of April 03, the death rate for COVID-19 positive patients in NYC was 2.99% [95% Clopper Pearson CI= 2.986, 2.997]. The rate is expected to be lower for our patient population. As such, 3 deaths among 100 patients will indicate a proportion of 3% [95% CI: 2.57%, 3.78%].

Analyses of Secondary Endpoints

Safety

Safety analyses will be conducted according to randomization assignment and treatment actually received. Adverse event rates will be calculated as the ratio of the total number of events over 14 days divided by total patient-days at risk for the specific event from randomization. A Poisson model with robust variance estimation will be used to compare SAEs between CPAP and control patients.

Time-to-events outcomes

Time from randomization to event outcomes (Hospitalization or ED visit, ICU admission, intubation and mechanical ventilation) within 14 days of randomization will be compared between randomization groups using a log-rank test or Gray's test in the presence of competing risk of death. In addition, survival at days 14 and 28 post-randomization will be described by Kaplan-Meier curves and a log-rank test will be used to compare survival between the two groups.

Respiratory Function

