- Improvement in oxygen saturation will be compared between randomization groups using linear mixed-effect models with patient as a random effect.
- Improvement in respiratory symptoms, as measured by the Clinical COPD Questionnaire, will be compared between randomization groups using linear mixed-effect models with patient as a random effect.

Conversion rate of family members

The conversion rates (yes/no) of family members in the two randomization groups will be compared using a Fisher's exact test. If there is sufficient variability, a zero-inflated count model may be considered as well.

Continuation of CPAP for greater than 72 hours

The proportion of patients in the CPAP group who elected to continue CPAP use after 72 hours will be estimated along with 95% Coppler-Pearson confidence intervals.

Exploratory Analyses

Exploratory analyses will be conducted similarly as the primary analysis except that it will be only in the control arm comparing OSA versus non-OSA patents and obese vs non-obese patients.

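### The one between-arm test named for adverse events pools all SAEs, so a real CPAP benefit on admissions can mask harm from the device

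*SAP*

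**What the plan says.** The SAP's *General Design Issues* makes safety, alongside efficacy, part of the primary objective. Its *Safety* paragraph has three elements:

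- Analysis sets: "Safety analyses will be conducted according to randomization assignment and treatment actually received".
- Adverse event rates: event counts over 14 days, "divided by total patient-days at risk for the specific event from randomization". No comparison is attached to these rates.
- One between-arm model: "A Poisson model with robust variance estimation will be used to compare SAEs between CPAP and control patients". Nothing separates events by cause or type.

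The protocol (section 10.2, *Adverse Events*) counts any unfavorable event "occurring in a participant at any stage of the study, whether or not considered related to the study", so COVID progression is an adverse event. Under *Clinical Endpoints* it adds: "Any reported AEs that meet the following are also clinical endpoints and will be reported on the End of Study form". The table there includes COVID worsening that leads to an emergency visit, admission, ICU care or intubation. It also includes events resulting in death. The SAP's primary composite contains "Hospital Admission (including ED visit) within 14 days of randomization" and "All-cause mortality within 14 days of randomization".

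**The concern.** An admission for worsening COVID is both an adverse event and a primary-endpoint event. If it is also classed as serious, the pooled SAE model partly repeats the efficacy comparison. Admissions avoided on CPAP then lower the CPAP count by as much as, or more than, device-caused events raise it. A report of no excess of SAEs on CPAP could come from efficacy rather than from the absence of device harm. It would then not support the safety half of the primary objective.

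**Working it through.** **Inputs from the documents.** 100 per arm and two-sided 0.05. The SAP power table gives a negative outcome in 25% of controls vs 9% on CPAP. *Sample Size and Power* cites about 25% later hospitalization among patients sent home.

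**The plan's own figure.** The documents give no operating characteristics for the SAE test. The power statement for the primary test does reproduce: enumerating both binomials for Fisher's exact test at 25% vs 9% gives power 0.830. The six table scenarios give 0.809 to 0.854, all above the stated 80%.

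**Assumptions.** Admission counts as serious. The composite pair 25% vs 9% stands in for admission; the 25% agrees with the cited hospitalization figure, but the 9% is a scenario. The documents give no rate for other SAEs, so I take 1% in control and 3% to 10% on CPAP. Each patient has at most one event of each kind, the two kinds are independent, and follow-up is equal.

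**Pooled test, one case by hand (other SAEs 1% vs 8%).**

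- Mean SAEs per patient: control 0.25 + 0.01 = 0.26; CPAP 0.09 + 0.08 = 0.17.
- Rate ratio: 0.17 / 0.26 = 0.654; log = −0.425.
- Variance per patient: control 0.25×0.75 + 0.01×0.99 = 0.1974; CPAP 0.09×0.91 + 0.08×0.92 = 0.1555.
- Robust SE of the log ratio: √[0.1974/(100×0.26²) + 0.1555/(100×0.17²)] = 0.288.
- Expected z: −0.425 / 0.288 = −1.47.

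The other SAEs are eight times as frequent on CPAP, yet the pooled test points towards CPAP.

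**Simulation.** 40,000 trials per row for the pooled test with robust variance. The separate test is a two-sided Fisher's exact test on the other SAEs only, by exact enumeration.

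| Other SAEs, control vs CPAP | Pooled ratio | Pooled test shows harm | Pooled test favors CPAP | Separate test shows harm |
|---|---|---|---|---|
| 1% vs 3% | 0.46 | about 0% | 69% | 3% |
| 1% vs 5% | 0.54 | about 0% | 52% | 19% |
| 1% vs 8% | 0.65 | about 0% | 30% | 57% |
| 1% vs 10% | 0.73 | 0.1% | 19% | 77% |

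**How far this depends on benefit.** With half the benefit (admission 25% vs 17%), the pooled test shows harm in about 2% of trials at 1% vs 8% and about 3% at 1% vs 10%. With no benefit (25% vs 25%) the figures are about 17% and 25%. They remain below the separate test because admissions add noise.

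**Where masking ends.** The pooled ratio reaches 1 when the excess of device SAEs equals the admissions avoided: 25 − 9 = 16 per 100 at the planned effect.

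**Limit of the separate test.** Even 0 events in 100 patients leaves a 95% Clopper-Pearson upper limit of 3.6%.

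**The case against.** The SAE model is not the only safety information planned. Household conversion is tested: "The conversion rates (yes/no) of family members in the two randomization groups will be compared using a Fisher's exact test". Survival is compared by log-rank test, and times to ICU admission and to intubation are compared separately. Event-specific rates will be calculated. The DMC Chair sees all deaths, unexpected SAEs and household conversions within 72 hours, and three CPAP deaths halt enrollment. All of this stands, so a reader should not infer that the SAE model is the only planned safety comparison. But none of these compares device harm to the CPAP user between arms. Conversion concerns the household, survival and ICU outcomes are disease outcomes, the rates carry no comparison, and DMC review is monitoring. Analysis by treatment received does not undo the pooling.

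A reader might also infer that SAEs here are mostly efficacy events. The documents do not establish that. SAE is undefined in the available text, the protocol's table lists adverse events rather than serious ones, and nothing makes either desaturation component serious. The table's version of the fall of more than 4% also requires breathing symptoms, which the endpoint does not.

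Nor does the table already isolate COVID worsening. One cell joins effects associated with CPAP to progression of underlying COVID, and deaths are listed without cause. A separate analysis cannot be built cleanly from it as it stands. Attribution would also be made by unblinded staff, who could code a device-caused admission as COVID worsening.

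Finally, the separate test is weak at low rates, so resting the safety conclusion on it alone would repeat the error of reading non-significance as safety.

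**Conclusion.** The point holds as a risk of masking. The only between-arm test the SAP names for adverse events pools events that can be efficacy outcomes with events that may be caused by the device. At the planned benefit and assumed other SAEs of 1% vs 8%, it would show harm in about 0% of trials and favor CPAP in about 30%, against about 57% detection by a separate comparison.

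This rests on admission counting as serious, on the composite scenario being used for admission, and on assumed rates of other SAEs. It does not follow that CPAP will look safe whatever the device does. In the main scenario the pooled test is non-significant in about 70% of trials, and masking weakens as the benefit shrinks or as device events approach the number of admissions avoided. At CPAP rates of 3% to 5% the separate test finds harm in only about 3% to 19% of trials, so it supplements the all-SAE result and cannot replace it.

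**What to change.** In SAP *Safety*:

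1. Define SAE, and say whether admission and ED visits qualify.
2. Keep the all-SAE Poisson model.
3. Add the same comparison, by randomized arm, for SAEs that are not primary-endpoint or COVID-progression events, with COVID deaths also left out. State the exclusion by cause. The composite puts no cause on admissions or deaths, so one attributed to CPAP should stay in this analysis; otherwise the rule removes the harm being sought.
4. Report both as a rate ratio and a rate difference with 95% confidence intervals. State that non-significance of either is not evidence of safety and that the two are read together.

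On the adverse event form, record CPAP-associated effects and COVID progression as separate items, and record a cause for each death. The reporting row of the protocol's table, whose layout is damaged in the available text, appears to require no reporting for the combined cell. Check this against section 10.6, which requires all events to be recorded and reported.

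The cost is one more model and a small form change; the design and sample size are unaffected. The downside is attribution by unblinded staff, which is why the all-SAE result stays in the report.

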#### **Secondary endpoints:**

• Time to ICU admission within 14 days of randomization

- Time to intubation and mechanical ventilation within 14 days of randomization
- Time to death within 14 and 28 days of randomization
  - Degree of improvement in oxygen saturation within 14 days of randomization
  - Improvement in respiratory symptoms of cough, shortness of breath, etc via respiratory symptom questionnaire within 14 days of randomization
  - Adverse events and conversion rates of COVID family members in CPAP vs control within 14 days of randomization
  - Percent of patients electing to continue CPAP for greater than 72 hours
  - Time to hospital admission or ED visit within 14 days of randomization

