- 8) All patients will be contacted every 6-12 hours to complete follow up assessments. These follow ups will be done via a phone call. If the timing of these follow ups fall between 10pm-6am, the follow up will be deferred until after 6am. After 72 hours, all patients will then be contacted daily until day 14 from randomization. After day 14, research staff will continue to monitor the medical charts for any visits to the hospital. One last contact will be made on day 28.
- 9) After 72 hours, patients will be asked to discontinue using the CPAP and pulse oximeter. If patients wish to continue to use the CPAP, they may do so for up to 7 days from time of randomization.
- 10) The research staff will continue to call all patients daily (after the 72 hour mark) to assess symptoms.
- 11) The patients can also choose to monitor their oxygen saturation beyond the 72 hours of treatment.
- 12) CPAP download is available continuously however we will download data on usage, pressure, leak daily and make adjustments to the mask or CPAP pressure as needed for patient comfort. For patients experiencing significant trouble tolerating high pressure, we will decrease CPAP from 8-10 cm to a fixed CPAP of 5 cm for 2-4 hours after which we will raise it back to 8-10cm for the

- duration of the study. If the patient is not able to tolerate the pressure again, we will reduce it back to 5cm of water pressure for several hours before increasing the pressure. This will be continued until the patient withdraws or 72 hours are completed, whichever occurs first.
- 13) Patients will be asked to track their own oxygen saturation using the provided pulse oximeter and report it when we contact them for the 6-12 hour follow up calls/surveys.
- 14) The sleep apnea test will provide continuous oxygen and breathing data for a period of 12 hours during the 72 hours and will also provide information on oxygen saturation while the patient is asleep.

The outline of the forms that correspond to the study visits can be found in the Appendix, Figure 1. All of these forms are subsequently included in the following appendicies.

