#### SCREENING VISIT

Upon reaching out to patient, the coordinator will confirm enrollment eligibility with the patient prior to consenting.

#### 7.3 VISIT 1

Visit 1 is performed by the coordinator. It consists of the following forms:

- Phone consent
- Enrollment Eligibility Form
- ER Admission Data Form
- Demographics and Subject History Form
- Participant Contact Form
- Medications Form
- CPAP and WatchPAT Assignment Form
- PROMIS questionnaire Form
- Randomization Form
- Respiratory Questionnaire Form
- 1. Once the Mount Sinai team has randomized patient, we will email [contact] with demographics and equipment ordered.
- 2. Community surgical will call patient to confirm address and information, they will then initialize the WatchPAT.
- 3. The pin used will be the DOB in the following format: MMDD
- 4. The pin will be written on the WatchPAT box as well
- 5. Community surgical will then deliver the equipment box to the patient. Patient will receive documents to sign via docusign.

- 6. Once delivery has been made, community surgical will notify PI
- 7. Community surgical will register patient on encoreanywhere once patient has been registered it will take approximately 24 hours before we are able to see the patient on our end

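### The mixed models for oxygen saturation and symptoms name no contrast, time structure, covariance, baseline or strata; a slope test from a random-intercept fit could be anti-conservative, and saturation after 72 hours rests on voluntary readings

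*SAP*

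**What the plan says.** SAP, Respiratory Function, covers two secondary endpoints in one sentence each. For saturation: "Improvement in oxygen saturation will be compared between randomization groups using linear mixed-effect models with patient as a random effect". For symptoms: "Improvement in respiratory symptoms, as measured by the Clinical COPD Questionnaire, will be compared between randomization groups using linear mixed-effect models", again with patient as a random effect. Nothing is said about fixed effects, time, a group-by-time term, residual covariance, robust variance, the role of baseline, or which quantity represents improvement. The randomization strata (BMI, gender and age; SAP, Randomization Design and Procedure) are given no role in these models.

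Protocol 1.3 lists the saturation endpoint as "Degree of improvement in oxygen saturation within 14 days of randomization".

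The data are serial. Protocol 7.1 item 8 says "All patients will be contacted every 6-12 hours to complete follow up assessments" and then "After 72 hours, all patients will then be contacted daily until day 14 from randomization". The Visits Figure shows six windows in the first 72 hours.

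For saturation, 7.1 item 9 says "After 72 hours, patients will be asked to discontinue using the CPAP and pulse oximeter", and item 11 adds "The patients can also choose to monitor their oxygen saturation beyond the 72 hours of treatment".

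On baseline, Protocol 7.3 lists a "Respiratory Questionnaire Form" at Visit 1. For saturation, the only pre-randomization value shown is the emergency-department reading on the ER Admission Data Form, taken with or without supplemental oxygen. Under 7.3 the equipment is ordered after randomization.

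**The concern.** Both endpoints are worded as improvement, and each patient contributes many readings, so a test of different change over time is a natural use of these models. The usual reading of a patient random effect is a random intercept, which treats any two readings in a patient as equally correlated. That is doubtful here. Readings hours apart are likely to be more alike than readings days apart, and Protocol 1.1 itself says decompensation tends to come 7-10 days into symptoms, so trajectories may differ between patients. If the equal-correlation assumption fails, some contrasts from a random-intercept fit have standard errors that are too small. With no contrast named, the choice among them could be made after the data are seen.

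Two further matters are separate from this. Baseline information and strata that cost nothing to use have no stated role, which loses precision. And the saturation endpoint extends 11 days beyond the period in which patients are asked to measure.

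**Working it through.** **Plan's own figures.** The SAP gives no standard deviation, correlation or power figure for these models, so the variance inputs below are assumptions. Its only power table concerns the primary Fisher test; exact power for the six scenarios is 0.830, 0.854, 0.843, 0.844, 0.809 and 0.833, all above the stated 80%.

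**Inputs.**
- From the documents: 100 patients per arm; six windows in 72 hours, taken at mid-window (9, 21, 33, 45, 57 and 69 hours); daily contacts on days 4 to 14, so 6 + 11 = 17 readings at most. For saturation the count lies between 6 and 17, because later readings are optional.
- Assumed: two-sided 0.05 for these models; total variance 1, split as 0.4 patient intercept, 0.4 serially correlated with correlation ρ at a one-day lag, and 0.2 independent error; ρ = 0.3, 0.5, 0.7.

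**Formulas (random-intercept fit, balanced data, no true effect).** Let V be the true within-patient covariance of the m readings, M the matrix that subtracts a patient's mean, t* the centred times and S = Σt*².
- Residual variance the model estimates: e = tr(MV)/(m − 1).
- Per-patient slope: model variance e/S; true variance t*′Vt*/S².
- First-to-last change over D days: model variance 2e; true variance 1.2 − 0.8ρ^D (D = 2.5 or 13.625).
- Single time point, with categorical time: model variance is the average of the visit variances; true variance is that visit's own. Both equal 1 here.
- Type I error = 2Φ(−1.96 × √(model variance / true variance)).

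Example, 17 readings, ρ = 0.5: S = 325.54 and e = 0.5441. Model variance of the slope is 0.5441/325.54 = 0.001671; true variance is 0.004090. The SE ratio is √(0.001671/0.004090) = 0.639, and 2Φ(−1.253) = 0.210.

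| Readings | ρ | Slope: SE ratio | Slope: type I | First-to-last change: type I | Single time point: type I |
|---|---|---|---|---|---|
| 6 | 0.3 | 0.795 | 0.119 | 0.076 | 0.050 |
| 6 | 0.5 | 0.766 | 0.133 | 0.086 | 0.050 |
| 6 | 0.7 | 0.771 | 0.131 | 0.088 | 0.050 |
| 17 | 0.3 | 0.749 | 0.142 | 0.056 | 0.050 |
| 17 | 0.5 | 0.639 | 0.210 | 0.062 | 0.050 |
| 17 | 0.7 | 0.542 | 0.288 | 0.075 | 0.050 |

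Simulation of 4,000 null trials per case agrees for the slope: 0.119, 0.127, 0.134 (6 readings) and 0.132, 0.226, 0.288 (17 readings).

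**Average difference.** The random-intercept model estimates the variance of patient means correctly in balanced data. Simulated type I error was 0.044 to 0.058 in every case tried.

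**Sensitivity to the assumed structure.** With patient-specific slopes instead of serial correlation (SD of total change 0.5, 1 or 2 residual SDs), the slope test gives 0.066, 0.108, 0.209 (6 readings) and 0.098, 0.213, 0.406 (17 readings). With equal correlation it gives 0.050. The single-time-point result also needs roughly constant variance over time. With slopes of SD 1, intercept and residual variance 1, and 17 readings, the last-visit variance is 2 + (14/13.625)² = 3.056 against an average of 2 + 60.07/13.625² = 2.324. The SE ratio is √(2.324/3.056) = 0.872, so type I error is 0.087.

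**Baseline.** For one follow-up reading with baseline correlation r, adjustment leaves 1 − r² of the unadjusted variance: 0.91, 0.75 and 0.51 at r = 0.3, 0.5 and 0.7, so the SE falls 5%, 13% and 29%. For a mean of six readings under equal correlation 0.5, the variance is (1 + 5 × 0.5)/6 = 0.583 unadjusted and 0.583 − 0.25 = 0.333 adjusted, an SE reduction of 24%. The gain from the strata cannot be computed, as their correlation with outcome is not given.

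**Saturation after 72 hours.** Set side by side, Protocol 1.3 defines the endpoint over 14 days, while 7.1 items 9 and 11 ask patients to stop the oximeter at 72 hours and make later readings optional. Under 7.1 item 5 saturation is reported through the follow-up survey, and the Follow-up Questionnaire is listed in 7.6 (days 4-7) but not in 7.7 (days 8-14). Whether another form captures saturation then is not shown.

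**The case against.** The strongest reply is that the SAP is brief rather than wrong. It does not say that patient is the only random term, that residuals are independent, or that baseline is excluded; improvement implies some baseline reference. Neither document names a slope test, and for an average difference the random-intercept standard error is sound. This stands. A reader might infer that the planned error bars are too small in general, but the documents do not support that, because the result depends on a contrast they do not define.

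A reader might also run the two complaints together. They act in opposite directions: omitting baseline makes a level comparison less precise and does not shrink its standard error.

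The baseline case is clear for symptoms only, assuming that the Visit 1 form is the Clinical COPD Questionnaire the SAP names. For saturation there is just a chart value, possibly taken on oxygen.

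Finally, optional monitoring applies to both arms, and a likelihood-based model tolerates readings missing at random. That also stands, but nothing in the documents makes missing-at-random likely. The trial is open-label and only the CPAP arm may continue treatment to day 7, so the decision to keep measuring could differ by arm and depend on symptoms.

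**Conclusion.** The point holds as an under-specified analysis of two secondary endpoints, with a conditional risk and two avoidable weaknesses.

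- **Type I error.** Roughly 12-29% if a random-intercept fit is used to test a linear group-by-time slope, about 6-9% for first-to-last change, and near 5% for an average or single-time-point difference. These figures rest on the assumed serial correlation; other structures move them in either direction, and the documents give no variances to settle it.
- **Precision.** Giving no role to the collected symptom baseline forgoes a variance reduction of r² for a single follow-up reading, 25% at an assumed r = 0.5. The strata would add an unknown amount.
- **Saturation window.** The 14-day endpoint and the reading schedule do not match. Self-selection after 72 hours is possible. To claim a bias of known direction or size would go beyond the documents.

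The primary Fisher test and its power are unaffected.

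**What to change.** In SAP, Respiratory Function, specify for each endpoint a repeated-measures model with:
- categorical time, treatment and treatment-by-time;
- the randomization strata as covariates;
- baseline as a covariate: the Visit 1 score for symptoms; for saturation, the emergency-department value with an indicator for supplemental oxygen;
- an unstructured or serial covariance, or robust standard errors. Unstructured is practical for six windows (6 × 7/2 = 21 parameters). For 17 readings it needs 17 × 18/2 = 153 parameters with 200 patients, so a serial structure in actual time with robust standard errors is the safer choice there.

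Name one contrast per endpoint: the arm difference at 72 hours for saturation and at day 14 for symptoms. Make the 72-hour window the inferential saturation analysis, report later readings descriptively by arm with the number of patients contributing, and align the saturation endpoint wording in Protocol 1.3.

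The cost is a small change to the SAP and to one protocol endpoint, made through the amendment process in Protocol 1.5. No new data or patients are needed. Intervals for any time-trend test become wider, and saturation after 72 hours loses its inferential status.
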